7.4. Reporting Pregnancy

If a participant becomes pregnant while taking study drug, the study treatment will be immediately discontinued, and the pregnancy must be reported to the sponsor or designee within 24 hours of awareness. The investigator will discuss the risks and concerns of study drug exposure to a developing fetus and counsel the participant and/or pregnant partner (or ensure such counseling is provided).

Reported pregnancy of a participant while participating in this study will be monitored for the full duration of the pregnancy, and/or followed through a definitive outcome (ie, birth or spontaneous or elective abortion). Pregnancies in partners of male study participants will similarly be monitored for the full duration of the pregnancy and/or followed through a definitive outcome (ie, birth or spontaneous or elective abortion).

An uncomplicated pregnancy will not be considered to be an AE or SAE. Pregnancy complications such as spontaneous abortion/miscarriage and congenital anomalies are considered to be SAEs and must be reported as described in Section 7.3. Note that an elective abortion is not considered to be an SAE. Pregnancy and pregnancy outcomes must be reported on a Pregnancy Notification or Pregnancy Outcome Form, respectively, and sent to the sponsor or designee within 24 hours of the investigator or site personnel learning of the pregnancy or pregnancy outcome.

The child born to a female participant or partner of a male participant exposed to study drug will be followed for 3 months after delivery. The outcome of any pregnancy and the presence or absence of any congenital abnormality will be recorded in the Pregnancy Outcome Form and reported to the sponsor or designee. Any congenital abnormalities in the offspring will be reported as an SAE and must be reported as described in Section 7.3.

Information regarding pregnancy testing (including definition of females of childbearing potential) is provided in Section 5.8 and Section 6.10.1. Highly effective means of contraception are listed in Section 5.9.

7.5. Reporting Overdose

If a participant takes more than the protocol-defined dose of study drug in a day and experiences a drug-related AE, this will be reported as an overdose and a protocol deviation. However, if the participant did not experience any AEs, this will only be reported as a protocol deviation.

The investigator will discuss the risks and concerns of study drug exposure with the participant. Parents, guardians, or participants are to be instructed to contact their study site immediately if an overdose of study drug is suspected. An overdose with AEs must be followed until the adverse effects are resolved or stabilized, or until reasonable attempts to determine resolution of the event are exhausted.

In the event of an overdose, the Investigator or treating physician should:

- Contact the study Medical Monitor within 24 hours.
- Closely monitor the participant for any AEs/SAEs and laboratory abnormalities as medically appropriate and follow up until resolution, stabilization, the event is otherwise explained, or the participant is lost to follow-up.
- Document the quantity of the excess dose as well as the duration of the overdose in the eCRF.
- Report to Sponsor Safety only when associated with an SAE.

7.6. Environmental Exposure, Exposure During Pregnancy or Breastfeeding, and Occupational Exposure

Note: This section is included to support Study transition to Pfizer Pharmacovigilance processes and systems.

Environmental exposure occurs when a person not enrolled in the study as a participant receives unplanned direct contact with or exposure to voxelotor. Such exposure may or may not lead to the occurrence of an AE or SAE. Persons at risk for environmental exposure include healthcare providers, family members, and others who may be exposed. An environmental exposure may include exposure during pregnancy (EDP), exposure during breastfeeding (EDB), and occupational exposure.

Any such exposures to voxelotor under study are reportable to the Sponsor or designee within 24 hours of Investigator awareness.

7.6.1. Exposure During Pregnancy

An EDP occurs if:

- A female participant is found to be pregnant while receiving or after discontinuing voxelotor.
- A male participant who is receiving or has discontinued voxelotor inseminates a female partner.
- A female nonparticipant is found to be pregnant while being exposed or having been exposed to voxelotor because of environmental exposure. Below is an example of environmental EDP:
 - A female family member of healthcare provider reports that she is pregnant after having been exposed to voxelotor by all possible routes of exposure, eg, ingestion, inhalation, or skin contact.
 - O A male family member or healthcare provider who has been exposed to voxelotor by all possible routes of exposure, eg, ingestion, inhalation, or skin contact, then inseminates his female partner prior to or around the time of conception.
- The Investigator must report EDP to the Sponsor or designee within 24 hours of the Investigator's awareness, irrespective of whether an SAE has occurred. The initial information submitted should include the anticipated date of delivery (see below of information related to termination of pregnancy).
- If EDP occurs in a participant/participant's partner, the Investigator must report this information to the Sponsor or designee regardless of whether an SAE has occurred. Details of the pregnancy will be collected after the start of voxelotor and until at least 140 days after the last dose.
- If EDP occurs in the setting of environmental exposure, the Investigator must report information to the Sponsor or designee. Since the exposure information does not pertain to the participant enrolled in the study, the information is not recorded on a CRF; however, a copy of the completed report is maintained in the Investigator site file.

Follow-up is conducted to obtain general information on the pregnancy and its outcome for all EDP reports with an unknown outcome. The Investigator will follow the pregnancy until completion (or until pregnancy termination) and notify the Sponsor or designee of the outcome as a follow-up to the initial report. In the case of a live birth, the structural integrity of the neonate can be assessed at the time of birth. In the event of a termination, the reason(s) for termination should be specified and, if clinically possible, the structural integrity of the terminated fetus should be assessed by gross visual inspection (unless pre-procedure test findings are conclusive for a congenital anomaly and the findings are reported).

Abnormal pregnancy outcomes are considered SAEs. If the outcome of the pregnancy meets the criterial for an SAE (ie, ectopic pregnancy, spontaneous abortion, intrauterine fetal demise, neonatal death, or congenital anomaly in a live-born baby, a terminated fetus, an intrauterine fetal demise, or a neonatal death), the Investigator should follow the procedures

for reporting SAEs. Additional information about pregnancy outcomes that are reported to the Sponsor or designee as SAEs follows:

- Spontaneous abortion including miscarriage and missed abortion should be reported as an SAE;
- Neonatal deaths that occur within 1 month of birth should be reported, without regard to causality, as SAEs. In addition, infant deaths after 1 month should be reported as SAEs when the Investigator assesses the infant death as related or possibly related to exposure to voxelotor.

Additional information regarding the EDP may be requested by the Sponsor. Further follow-up of birth outcomes will be handled on a case-by-case basis (eg, follow-up on preterm infants to identify developmental delays). In the case of paternal exposure, the Investigator will provide the participant with the Parental Partner: Information Sheet and Informed Consent Form to deliver to his partner. The Investigator must document in the source documents that the participant was given the Pregnant Partner Release of Information Form to provide to his partner.

7.6.2. Exposure During Breastfeeding

An EDB occurs if:

- A female participant is found to be breastfeeding while receiving or after discontinuing voxelotor.
- A female nonparticipant is found to be breastfeeding while exposed or having been exposed to voxelotor (ie, environmental exposure). An example of environmental EDB is a female family member or healthcare provider who reports that she is breastfeeding after having been exposed to voxelotor by all possible routes of exposure, eg, ingestion, inhalation, or skin contact.

The Investigator must report EDB to the Sponsor or designee within 24 hours of the Investigator's awareness, irrespective of whether an SAE has occurred. When EDB occurs in the setting of environmental exposure, the exposure information does not pertain to the participant enrolled in the study, so the information is not recorded on a CRF. However, a copy of the completed report is maintained in the Investigator site file.

7.6.3. Occupational Exposure

The Investigator must report any instance of occupational exposure to the Sponsor or designee within 24 hours of the Investigator's awareness regardless of whether there is an associated SAE. Since the information about the occupational exposure does not pertain to a participant enrolled in the study, the information is not recorded on a CRF; however, a copy of the completed report is maintained in the Investigator site file.

7.7. Medication Errors

Note: This section is included to support Study transition to Pfizer Pharmacovigilance processes and systems.

Medication errors may result from the administration or consumption of voxelotor by the wrong participant, or at the wrong time, or at the wrong dosage strength.

Medication errors are recorded and reported as follows:

Table 12: Reporting of Medication Errors

Recorded on the Medication Page of the CRF	Recorded on the Adverse Event Page of the CRF	Reported to the Sponsor Within 24 Hours of Awareness		
All (regardless of whether associated with an AE)	Any AE or SAE associated with the medication error	Only if associated with an SAE		

Abbreviations: AE, adverse event; CRF, case report form; SAE, serious adverse event.

Medication errors include:

- Medication errors involving participant exposure to the study drug
- Potential medication errors or uses outside of what is foreseen in the protocol that do or do not involve the study participant;
- The administration of an incorrect dosage;
- The administration of expired study drug;
- The administration of an incorrect study drug;
- The administration of study drug that has undergone temperature excursion from the specified storage range unless it is determined by the Sponsor that the study drug under question is acceptable to use.

Whether or not the medication error is accompanied by an AE, as determined by the Investigator, such medication errors occurring to a study participant are recorded on the medication page of the CRF, and, if applicable, any associated serious and nonserious AE(s) are recorded on the AE page of the CRF.

In the event of a medication dosing error, the Sponsor or designee should be notified within 24 hours.

Medication errors resulting in an AE or SAE should be reported to the Sponsor or designee within 24 hours via the CRF.

7.8. Data and Safety Monitoring Board

An independent Data and Safety Monitoring Board (DSMB) will monitor safety data from Study GBT440-038 for participants whose originating study was Study GBT440-032. The responsibilities, and other details of the DSMB are described in the DSMB Charter.

The DSMB will be comprised of medical and statistical representatives and may provide recommendations to the Sponsor regarding stopping or modifying the study for participants from Study GBT440-032.

Sites and their respective IRBs/ECs will be informed of the DSMB recommendations if the recommendations affect study participant safety and/or lead to changes to the study conduct.

8. DATA ANALYSIS AND STATISTICAL PLANS

Statistical programming and analyses will be performed using established statistical methods.

Study data will be reported using summary tables, figures, and select data listings. Continuous variables will be summarized using mean, standard deviation, median, minimum, and maximum. Categorical variables will be summarized by presenting the number (frequency) and percentage in each category. All statistical analyses conducted will be descriptive and no formal statistical tests are planned. As appropriate, study data may be summarized separately based on the antecedent study.

8.1. Endpoints

8.1.1. Safety

TEAEs and SAEs

8.1.2. Sickle Cell Disease–Related Complications

• Frequency of SCD-related complications

8.2. Sample Size

The sample size for this study will not exceed total enrollment in the GBT-sponsored voxelotor clinical studies.

8.3. Populations for Analysis

Safety Population: All participants who receive at least 1 dose of study drug in this study will be included in the safety population.

8.4. Analysis of Safety

8.4.1. Adverse Events

Adverse events will be classified using the Medical Dictionary for Regulatory Activities (MedDRA). A TEAE is defined as an AE that emerges on or after initiation of study drug (having been absent pretreatment), or an AE that existed pretreatment and worsened on treatment (relative to the pretreatment state). The incidence of TEAEs will be tabulated by system-organ-class (SOC), Preferred Term, severity, and relationship to study drug (as assessed by the investigator).

8.4.2. Clinical Laboratory Tests and Vital Signs

Clinical laboratory test and vital sign results over time will be summarized using descriptive statistics.

8.4.3. Frequency of Sickle Cell Disease–Related Complications

Sickle cell disease-related complications over the course of the treatment period will be recorded for each participant. SCD-related complications may include, but are not limited to, the following: sickle cell anemia with crisis, ACS, pneumonia, priapism, splenic or hepatic sequestrations, stroke, leg ulcers, and osteonecrosis. SCD-related complications will be summarized in a manner similar to that for TEAEs, as described in Section 8.4.1.

8.5. Handling of Missing Data

Data will be summarized as observed with no imputation for missing values, except for partially missing dates.

[figure not shown]
8.6. Pharmacokinetic Sample Collection and Analysis

Whole blood and plasma concentrations of participants taking the modified dose of voxelotor dispersible tablet will be collected predose on the day participants switch to modified dose dispersible tablet (Day of Switch), 14 days after the switch date (14 Days Post-Switch), and 12 weeks after the switch date (12 Weeks Post-Switch) at select sites (Figure 1, Appendix B). Participants should be encouraged to take their voxelotor dose at a regular time every day. However, on the days of PK sample collection, the PK sample should be obtained approximately 24 hours after the subject's administration of voxelotor. Therefore, the site should instruct the subject to take the dose approximately 24 hours prior to their scheduled visit The participant or their caregiver are to record the time of the voxelotor dose taken prior to each of these visits.

Whole blood and plasma voxelotor levels will be evaluated by comparison of predose voxelotor concentration on 14 Days Post-Switch and 12 Weeks Post-Switch with predose voxelotor concentration on the Day of Switch.

A population pharmacokinetic (PK) analysis may be conducted using nonlinear mixed effects modeling.

Figure 1: Pharmacokinetic Sample Collection

* Day of Switch is a regularly scheduled visit (Day 1 or other) at which participant starts modified dose dispersible tablet.

9. DIRECT ACCESS TO SOURCE DATA/DOCUMENTS

9.1. Source Data

Original documents, data, records (eg, clinic records, laboratory notes, memoranda, participant diaries or evaluation checklists, pharmacy dispensing records, recorded data from automated instruments, copies or transcriptions certified after verification as being accurate and complete, microfiches, photographic negatives, microfilm or magnetic media, X-rays, participant files, and records kept at the pharmacy, laboratories, and medico-technical departments involved in the clinical study), and all relevant sections of the participant's medical records and all other data collection made specific to this study constitute source documents.

The completed eCRF is not a source document. The investigator/institution will permit study-related monitoring, audits, IRB/EC review, and regulatory inspection by providing direct access to source documents.

9.2. Data Collection

The investigator will be responsible for maintaining accurate and adequate source documents from which data will be transcribed to eCRFs designed to record data pertinent to this study. All relevant observations and data related to the study will be recorded. This will include medical and medication history, PEs, a checklist of inclusion and exclusion criteria, investigational treatment administration, a record of sample collection, clinical assessments, AEs, and final evaluation(s). The monitor will review all eCRFs and compare data to those contained in clinic notes and participants' source documents/medical records.

Data for each participant will be recorded on the eCRF. An eCRF must be completed for every participant enrolled in the study. When data are complete, the investigator or medically qualified subinvestigator listed on Form Food and Drug Administration (FDA) 1572 (or Investigator's Agreement if applicable) will apply his/her signature on the eCRF indicating he/she has reviewed and approves of the data collected on the eCRF.

10. QUALITY CONTROL AND QUALITY ASSURANCE

10.1. Monitoring

Site personnel will be provided with training on how to collect quality data for the study, and a sponsor monitor or designee will be contacting the site periodically to review study conduct and data recorded at the site. At the sponsor's discretion, on-site monitoring visits may be conducted prestudy, during the study, and following study completion. These visits are to provide the sponsor with the opportunity to evaluate study progress; verify the accuracy and completeness of source data and eCRFs; and ensure that all protocol and Good Clinical Practice (GCP) requirements, applicable United States (US) FDA or country-specific regulations, and investigator obligations are being fulfilled. The sponsor may terminate study participation by a clinical study site if study-site personnel do not follow the protocol or GCP. Additionally, individual participants may be excluded if a medical record review indicates protocol violations or if other factors appear to jeopardize the validity of the study.

The investigator agrees to cooperate with the monitor to ensure that any problems detected during the course of these monitoring visits are resolved.

10.2. Quality Control and Quality Assurance

The sponsor may conduct quality assurance audits of this study. If such an audit occurs, the investigator agrees to allow the auditor direct access to all relevant documents (eg, all participant records, medical records, and eCRFs) and access to all corresponding portions of the office, clinic, laboratory, or pharmacy that may have been involved with the study. The investigator will allocate his or her time and that of the study-site personnel to the auditor to discuss findings and any relevant issues.

In addition, regulatory agencies may conduct a regulatory inspection of this study. If such an inspection occurs, the investigator agrees to notify the sponsor upon notification by the regulatory agency. The investigator agrees to allow the inspector direct access to all relevant documents and to allocate his or her time and that of the study-site personnel to the inspector to discuss findings and any relevant issues. The investigator will allow sponsor personnel to be present as an observer during a regulatory inspection, if requested.

10.3. Laboratory Accreditation

The laboratory facility used for analysis of clinical laboratory samples must provide evidence of adequate licensure or accreditation. Copies of laboratory certification, licensure, and reference ranges (as appropriate) will be supplied to the sponsor prior to study initiation. The sponsor or designee should be notified of any changes in reference range values or certification/license renewal during the course of the study.

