3. INVESTIGATIONAL PLAN

3.1. Study Design

This multicenter, nonrandomized OLE study is designed to assess the safety of, and SCD-related complications with, long-term treatment with voxelotor in participants with SCD. The study will be conducted globally and will be available to eligible participants from GBT-sponsored voxelotor clinical studies. Participants must have completed participation in their originating clinical study and must meet the entry criteria for this study to be eligible for enrollment (see Section 4). The study will be conducted at up to approximately 70 global clinical sites, and up to approximately 600 participants will be enrolled. The collection of voxelotor predose whole blood and plasma concentrations in participants receiving a modified dose of voxelotor dispersible tablets will be conducted in approximately 20 participants at selected sites.

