6.10. Clinical Laboratory Assessments

Blood and urine samples for clinical laboratory tests will be collected at the time points indicated in the Schedule of Assessments (Appendix A).

The clinical laboratory tests that will be performed are listed in Table 9. All tests will be performed at the local clinical laboratory.

Table 9: Clinical Laboratory Tests

He	matology	Serum Chemistry Other
_	Hematocrit	 Alanine aminotransferase Urine pregnancy test ^a
_	Hemoglobin	- Albumin ^b
_	Mean corpuscular hemoglobin	 Alkaline phosphatase
	concentration	 Aspartate aminotransferase
-	Mean corpuscular volume	- Bicarbonate b, c
_	Platelet count	Bilirubin (total, direct, and
_	RBC count	indirect)
_	RBC distribution width	- Blood urea nitrogen
_	Reticulocyte count	- Calcium ^b
	(absolute and percent)	- Chloride ^b
_	WBC count with differential	- Creatinine
	(basophils, eosinophils,	- Glucose ^b
	neutrophils, monocytes,	 Lactate dehydrogenase
	lymphocytes)	- Potassium ^b
		- Sodium ^b

Abbreviations: RBC, red blood cell; WBC, white blood cell.

It is the responsibility of the Investigator or designee to assess the clinical significance of all abnormal clinical laboratory values as defined by the list of normal values on file for the local clinical laboratory. All clinically significant laboratory value abnormalities are to be recorded as AEs.

Additional and repeat clinical laboratory tests for the evaluation of abnormal results and/or AEs during the study may be performed at the discretion of the Investigator or upon request of the sponsor.

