6. GENERAL STATISTICAL CONSIDERATIONS

6.1 Sample Size Considerations

The total sample size for this study will not exceed total enrollment in the originating GBT/Pfizer-sponsored voxelotor clinical studies.

In addition, the collection of voxelotor predose whole blood and plasma concentrations in participants receiving a modified dose of voxelotor dispersible tablets will be conducted in approximately 20 participants at selected sites.

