8. STATISTICAL METHODS

Statistical analyses will be performed using SAS® Version 9.4 or higher.

Continuous variables will be descriptively summarized using number of participants (n), mean, standard deviation (SD), median, minimum, and maximum. Categorical variables will be descriptively summarized by presenting the number (frequency) and percentage in each category. All statistical analyses conducted will be descriptive and no formal statistical tests are planned.

Additionally, for the subset of participants receiving the modified dose of voxelotor in dispersible tablet in this study, separate summaries will be provided for selected CRF data (e.g., TEAEs).

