8.2.5 Clinical Laboratory Assessments

The following protocol-specified clinical laboratory findings will be summarized using descriptive statistics.

- 1. Hematology:
 - a. Hemoglobin (Hb)
 - b. Neutrophils (absolute and %)
 - c. Platelets
 - d. Reticulocyte count (percent and absolute reticulocyte)
 - e. White blood cells (WBCs)
- 2. Chemistry and Liver Function Tests:
 - a. Alkaline phosphatase
 - b. Alanine aminotransferase (ALT)
 - c. Aspartate aminotransferase (AST)
 - d. Potassium
 - e. Indirect bilirubin
 - f. Total bilirubin
 - g. Lactate dehydrogenase (LDH)
 - h. Serum Erythropoietin

Change from Day 1 and the percent change from Day 1 will be summarized for the above laboratory results. Analyte units will be converted to International System of Units (SI). The end-of-treatment assessments performed upon completion of the antecedent study may serve as the Day 1 assessments for Study GBT440-038.

Participant listings of laboratory data will include a separate listing for clinically significant laboratory results.

If indirect bilirubin is missing and direct and total bilirubin are collected, indirect can be calculated as:

 $Indirect \ Bilirubin = Total \ Bilirubin - Direct \ Bilirubin.$

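### SAP 8.2.5 summarises liver enzymes, LDH and bilirubin from local laboratories only as pooled raw values after SI conversion, so no planned table uses the ULN scale on which the protocol judges liver safety

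*Protocol*

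**What the plan says.** **Where samples are assayed.** Protocol 6.10: "All tests will be performed at the local clinical laboratory". Protocol 3.1: "The study will be conducted at up to approximately 70 global clinical sites, and up to approximately 600 participants will be enrolled".

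**What the sponsor holds.** Protocol 10.3: "Copies of laboratory certification, licensure, and reference ranges (as appropriate) will be supplied to the sponsor prior to study initiation". It adds: "The sponsor or designee should be notified of any changes in reference range values or certification/license renewal during the course of the study".

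**The scale used for individual participants.** Protocol 6.10 has the investigator judge abnormal values against the local laboratory's normal values. Table 6 sets ALT actions at 3, 5 and 8 × ULN. Appendix C defines potential liver-injury cases by AST or ALT at 3 × ULN with total bilirubin at 2 × ULN, and adjusts both for raised baselines. Since every test is local, the ULN in these rules is presumably the local one.

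**The scale used for the tables.** SAP 8.2.5 gives descriptive statistics, change and percent change from Day 1 for alkaline phosphatase, ALT, AST, LDH and indirect and total bilirubin, among others. Its only step across laboratories is "Analyte units will be converted to International System of Units (SI". It also provides listings, one of them for clinically significant results. The SAP has no summary in multiples of ULN, no shift table, no threshold count and no summary by laboratory.

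**Day 1.** SAP 8.2.5: "The end-of-treatment assessments performed upon completion of the antecedent study may serve as the Day 1 assessments for Study GBT440-038". Protocol Section 6 says the same. Neither says which laboratory ran those samples.

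**The concern.** The protocol and the SAP use different scales for the same measurements. Decisions on a participant are made relative to the ULN, while the study-level tables are in raw units pooled over laboratories. Converting to SI puts results in a common unit. It does not make two enzyme-activity methods read alike, and it does not align their reference ranges.

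Three things follow for the tables:

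- Visit means and SDs contain laboratory differences as well as biology.
- Treatment is open-ended (Protocol 3.2), so participants and sites leave at different times. The mix of laboratories, and with it the visit mean, can move without any biological change. There is no control arm in which the same drift would show.
- A reader cannot tell how many participants reached 3, 5 or 8 × ULN.

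Long-term safety is the study objective, and laboratory tests are a named parameter of it. Protocol 1.4 also lists LDH and indirect bilirubin as measures of haemolysis, so the point reaches beyond liver safety.

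**Working it through.** There is no figure in the plan to reproduce. SAP 8 states "All statistical analyses conducted will be descriptive and no formal statistical tests are planned", and SAP 6.1 sets a ceiling on enrolment rather than a calculated size. What follows is an illustration.

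**From the documents:** about 70 sites and 600 participants at most, or 600/70 ≈ 8.6 per site.

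**Assumed:** one laboratory per site; observed value = true value × laboratory factor; between-laboratory CV of 10%, 20% or 30%; between-participant CV of 35%; mean ALT of 30 U/L; no true change over time.

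**1. Pooled SD.** Ratio to the SD without laboratory differences = √(0.35² + CV² + (0.35·CV)²) / 0.35.
- CV 10%: √0.1337 / 0.35 = 1.04
- CV 20%: √0.1674 / 0.35 = 1.17
- CV 30%: √0.2235 / 0.35 = 1.35

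**2. Drift with site mix.** Suppose half the participants are at laboratories with factor 0.9 and half at laboratories with factor 1.1. The mean is 30 × (0.5 × 0.9 + 0.5 × 1.1) = 30 U/L. If the 0.9 sites leave, it becomes 30 × 1.1 = 33 U/L, a 10% rise with nothing changed in any participant.

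**3. Reading the ULN scale from raw units.** An ALT of 120 U/L at assumed ULNs of 35, 40, 45 and 55 U/L is 3.43, 3.00, 2.67 and 2.18 × ULN. The same value is at or above the protocol's 3 × level in two laboratories and below it in the other two. A raw summary cannot separate these.

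**4. Change from Day 1, same laboratory.** The factor cancels in percent change, so the spurious change is 0. It still scales the absolute change.

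**5. Change from Day 1, different laboratories.** This is possible under the text but not stated to occur. If the two factors are independent lognormals with equal CV, the expected ratio is 1 + CV² and the median ratio is 1. Even if every pair crossed laboratories:
- the mean percent change shifts by +1% (CV 10%) or +4% (CV 20%), and the median by 0;
- individual changes scatter, with a 95% range of exp(±1.96·√(2·ln(1 + CV²))) − 1, which is −24% to +32% at CV 10% and −42% to +73% at CV 20%.

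A larger mean shift needs a common direction. If a share f of participants has follow-up/Day 1 factor r, the mean shift is 100·f·(r − 1)%. For r from 0.8 to 1.25, f = 0.25 gives −5% to +6.25%, and f = 1 gives −20% to +25%.

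**6. With the fix.** If each value is divided by its own laboratory's ULN, and that ULN tracks the assay factor, r becomes 1 and the spurious change is 0. Where the ULN does not track the assay, the correction is partial.

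**The case against.** **Individual safety already runs on local ranges.** This is right. Investigators use local normal values, and Table 6 and Appendix C use ULN multiples. Clinically significant abnormalities become adverse events, potential Hy's law cases are SAEs, and both reach the tables in SAP 8.2.2. A reader might infer that liver cases would be missed; the documents do not support that. What remains is that adverse events are tabulated by organ class, preferred term and maximum severity after an investigator's judgement, and Protocol 7.2.3 asks for the diagnosis where there is one. None of this gives an objective count at each ULN multiple.

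**Nothing says that Day 1 came from another laboratory.** This is also right. A reader might infer that laboratory differences will appear as change on treatment. The documents permit cross-laboratory pairs but do not say that any exist. Section 6 prefers enrolment on the day of the last antecedent visit, and Appendix A note a waives repeat tests only when Day 1 falls on that date. Under random differences the mean shift is small. The wide ranges in step 5 are scatter between individuals, not bias in a summary.

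**No inference is planned.** A reader might also infer that the precision of the laboratory means will be overstated, because participants cluster within laboratories. SAP 8 plans no SE or confidence interval for laboratory values, so that criticism has no target.

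**ULN scaling has its own flaws.** Laboratories may use different reference populations, and a child crossing an age band can show a change in × ULN with no change in the value. This stands, and is why the raw summaries should be kept.

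**Conclusion.** The point holds as a gap in the aggregate laboratory summaries, and closing it is a cheap improvement. The local testing, the ULN-based liver rules, the ranges sent to the sponsor, and SI conversion as the only harmonisation are all in the text.

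The size cannot be derived from the documents. Steps 1 to 3 rest on assumed CVs, laboratory factors and ULNs, and on one laboratory per site, which is inferred from the site count. The firmest part needs no assumption about size: no planned table shows how many participants reached the levels on which the protocol acts.

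The effect on change from Day 1 is conditional on cross-laboratory pairs existing, and its size is unknown. No error rate or sample size is touched, and no clinical rule needs to change.

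**What to change.** Add to SAP 8.2.5:

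> For ALT, AST, alkaline phosphatase, LDH and total bilirubin (and indirect bilirubin where a local ULN exists), values will also be expressed as multiples of the local laboratory ULN applicable on the sample date, using the reference ranges supplied under protocol Section 10.3. Observed × ULN values will be summarised. The number and percentage of participants whose maximum post-Day 1 value reaches the × ULN levels already used in Table 6 and Appendix C will be tabulated, together with shifts from Day 1 relative to the normal range. Raw-unit summaries will be kept for all participants. Pairs with Day 1 and follow-up from different laboratories will be counted, and change from Day 1 will be repeated excluding them as a sensitivity summary.

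The threshold counts apply mainly to ALT, AST and total bilirubin. Table 6 and Appendix C set no level for LDH or indirect bilirubin, so those would have values and shifts only.

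Keeping every pair in the main raw summary respects Protocol 8.5, which summarises data as observed. Section 10.3 needs no change, because it already provides for the ranges and for notice of changes.

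**Cost:** SAP wording, a dated reference-range table linked to each result, and programming. No new samples or visits are needed. The limits of ULN scaling should be stated in a table footnote.
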